### **7.3 Evaluation During Study Intervention**

7.3.1 Telephone calls (these will occur regardless of use of phone app).

Phone call for compliance, changes in concomitant medications, and adverse event monitoring (call may be substituted by email if convenient for the subject)

- Week 1, week 4, and week 8 (week 4 and 8 calls as appropriate based on surgery date). A window of  $\pm 3$  days is allowed.

Please refer to Appendix D for suggested language for participant communications.

### **7.4 Evaluation at Completion of Study Intervention**

#### Study Visit 1: Day of Surgery (following 4-10 weeks of study agent)

- Physical Exam including vitals. The source document for this may be anesthesia or surgery H&P, completed within 14 days prior to surgery.
- BESS questionnaire\*
- Toxicity and AE Assessment\*
- Record Concomitant Medications\*
- Collection of agent and compliance check\* - Capsule count and study gel application
- Clinical Labs – including CBC and Chemistry Panel
- Blood collection for research purposes:

- Two 2.7 mL Blue Top tube (citrate) to obtain plasma for coagulation panel.
- Two 10mL Lavender top tubes (K2EDTA) to obtain plasma and buffy coat or white blood cells (WBCs) for following purposes:
  - a) Plasma for measuring tamoxifen and its metabolites [tamoxifen, *N*-desmethyl tamoxifen, (*E*) 4-OHT, (*Z*) 4-OHT, (*E*) endoxifen, and (*Z*) endoxifen].
  - b) Plasma for measuring steroid hormones (estradiol, progesterone).
  - c) Plasma for measuring IGF-1, IGFBP-3, and SHBG.
  - d) Buffy coat will be saved for DNA/RNA isolation.
- Collection of surgical specimen for drug concentration assay – see section 10 for details.
- Pregnancy Test (only offered for premenopausal women with child-bearing potential).
- Recording of depth of lesion from skin, based on wire localization films in subjects undergoing breast conserving surgery, or on direct measurement during grossing of mastectomy slices in subjects undergoing mastectomy.
- For Premenopausal women, record last menstrual period and estimated next menstrual period dates. Confirm and record actual menstrual period date at Visit 2 or the final phone call.

\*BESS Questionnaire, toxicity and AE assessment, review of concomitant medications, and compliance check (collection and review of study agent) may be performed at either Visit 1 (day of surgery) or on the day prior to surgery.

## 7.5 Post-intervention Follow-up Period

### Study Visit 2: Post-surgical visit (within 21 days after surgery)

- Physical exam including vitals.)
- Toxicity and AE assessment
- For premenopausal women, confirm and record actual menstrual period date or estimated next period date. Follow up at the final phone call if no period has occurred since surgery.
- Obtain surgical pathology report to document pathologic features including DCIS size, grade, and presence of invasion.
- Start process of requesting paraffin blocks of surgical specimen or sections of the paraffin block, from institutions that do not allow release of paraffin blocks.

### Follow-up phone call (up to 35 days after Study Visit 2)

- Assess date of last menstrual period for premenopausal participants whose last menstrual period did not occur between surgery and Visit 2. This call should take place 14-21 days after the expected period date, or 28-35 days after Visit 2 if no expected period date is known.
- Assemble and mail all study-related samples (blood, fresh tissue, FFPE blocks or sections). Please refer to Appendix D for suggested language for participant communications.

## 7.6 Methods for Clinical Procedures

### 7.6.1. Review of radiologic-pathologic concordance by surgeon and radiologist.

The treating surgeon will confer with the breast radiologist to verify that pathologic findings are concordant with imaging assessment, all clinically indicated imaging has been performed, and no evidence of invasive disease on the ipsilateral side is present. The size measured on imaging studies will also be confirmed at this time.

### 7.6.2 Assessment of pathologic size

The pathologist signing out the surgical pathology specimen will use the following protocol for size assessment: a) using the slide with maximal disease, report the span of disease in two dimensions; b) report the number of blocks with disease; c) estimate the thickness of tissue per block, multiple the number of blocks by the thickness, report this product as the third dimension. The pathologic size of the DCIS lesion will be recorded as the longest dimension.

## **8. CRITERIA FOR EVALUATION AND ENDPOINT DEFINITION**

### **8.1 Primary Endpoint**

The primary objective of this study will be to demonstrate that 2mg once daily per breast of 4-OHT topical gel results in a reduction in the Ki-67 labeling index of DCIS lesions that is not inferior to that seen with 20mg daily oral TAM for 4 to 10 weeks, when comparing the base-line diagnostic core biopsy (pre-therapy) sample to the therapeutic surgical excision (post-therapy) sample.

Ki67 labelling will be assessed by standard immunohistochemistry as used in our previous study [35] and quantified by computer-assisted image analysis at the Northwestern University Pathology Core Facility. [name] (study pathologist at NU) will perform designation of regions of interest for digital scoring. The Ki67 LI in the diagnostic core needle biopsy will be compared to that in the excisional specimen, with the pathology team blinded to the study groups.

### **8.2 Secondary and Exploratory Endpoints**

- 8.2.1 Oncotype DCIS-Score (validated RT-PCR assay for 12 genes)[53]. This will be performed by Exact Sciences, according to their highly reproducible and well-validated methods.
- 8.2.2 Breast tissue and plasma levels of TAM and its metabolites [N-desmethyl tamoxifen (NDT), (E) and (Z) isomers of 4-hydroxytamoxifen (4-OHT), N- desmethyl-4-hydroxytamoxifen (Endoxifen)] to be performed at Hormone Laboratory of Haukeland University Hospital, Norway.
- 8.2.3 Ki67 LI in terminal duct lobular units, applying the same methods as described for measurement of the primary endpoint (KI67 LI in the DCIS lesions).
- 8.2.4 Plasma proteins involved in coagulation: Factors VIII and IX, von Willebrand Factor, total protein S to be performed at the Northwestern Memorial Hospital Hemostasis Lab and Quest Diagnostics.
- 8.2.5 Plasma markers of systemic estrogenic effect (IGF-1, IGFBP-3, and SHBG) to be performed at the Northwestern University Comprehensive Metabolic Core Lab.
- 8.2.6 Patient reported symptoms as captured in the BESS questionnaire, and skin reactions to 4-OHT gel, as in our prior study of 4-OHT gel [35].
- 8.2.7 IHC markers: CD-68 macrophage marker as a surrogate for response to therapy. p16 and COX-2 [46]. [name] (study pathologist) will mark the DCIS lesion of H&E slides to be evaluated by biomarker IHC assays. IHC staining and scoring will be performed by the Northwestern University Pathology Core Facility.
- 8.2.8 Plasma levels of steroid hormones (estradiol and progesterone) in pre-therapy and post-therapy samples, to be measured by Hormone Laboratory of Haukeland University Hospital, Norway.
- 8.2.9 Breast tissue levels of steroid hormones (estradiol and progesterone) in post-therapy samples , to be measured by Hormone Laboratory of Haukeland University Hospital, Norway.
- 8.2.10 Fraction of subjects with “no residual DCIS” in surgical sample. This will be assessed by the study pathologist ([name]) on the surgical excisional sample.

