### *3.7 Description of measurements taken to meet study objectives*

*Screen 1:* at entry, for consent, medical history including date of last period and menopause determination, pregnancy test (if needed), breast cup size, body mass index, explanation of gel application, baseline symptom assessment (BESS questionnaire), and blood draw. After randomization, the study coordinator will request the paraffin blocks of the diagnostic core needle biopsy (DCNB). The study consent will include specific permission from the subject, to allow the DCNB block, and a selected surgical block to be released to Northwestern University (NU). These will be mailed to NU per instructions in the lab manual. Institutions that do not allow release of DCNB blocks, will provide multiple unstained sections of the DCNB block as detailed in Section 10.2.3.

*Study Visit 1:* on the day of surgery for blood draw, BESS questionnaire, medical history, symptoms assessment, and collection of surgical tissue sample (since the blood and surgical samples must be collected on the same day). Breast adipose and parenchymal tissue excised from multiple locations will be snap frozen with liquid nitrogen and stored at -80°C for measurement of TAM metabolites. A portion of each sample will be formalin-fixed for assessment of tissue composition (see Section 10 and Figure 2A).

*Study Visit 2:* the post-operative visit, up to 21 days post-surgery, to document resolution of study related

symptoms. Visit 2 will also serve as the trigger for the study coordinator to request the paraffin blocks of the surgical sample, since the final pathology report will have been issued at this point. These will be mailed, along with other study samples, in a single shipment as each participant completes the study, per instructions in the lab manual. Institutions that do not allow release of paraffin blocks, will provide multiple unstained sections of the paraffin block as detailed in Section 10.2.3. A final phone call will be made up to 35 days following Study Visit 2 to premenopausal women whose last menstrual period did not occur between surgery and Study Visit 2.

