## 10.2 Collection and Handling Procedures

### 10.2.1 Amount of sample

- Blood samples (Screen 1 and Study Visit 1): Blood samples will be collected with an appropriate type of anti-coagulants, and processed as described in session 7.1 (the schedule of event table footnote #5 and #11). 1) **Two** 2.7mL blue top tubes (citrate) to obtain plasma for coagulation panel assays. Each tube must be a full draw. 1mL each will be aliquoted in a 1.8 mL size cryo-vial. We will make as many aliquots as available. The last aliquot may not be enough for 1 mL, but save it as well and record approximate volume available. 2) **Two** 10 mL lavender top tubes (K2EDTA) to obtain plasma and buffy coat. We will get approximately 3~4 mL plasma from one lavender top tube. 1mL each will be aliquoted in a 1.8 mL size cryo-vial. We will make as many aliquots as available. The last aliquot may not be enough for 1 mL, but save it as well and record approximate volume available. Plasma aliquots will be used for IGF-1 and SHBG assays (Screen 1 and Study Visit 1); for steroid hormone assays (estradiol, progesterone, and dehydroepiandrosterone (DHEA), androstenedione, and testosterone (Screen 1 and Study Visit 1); and for measuring tamoxifen and its metabolites [tamoxifen, N-desmethyl tamoxifen, (E) 4-OHT, (Z) 4-OHT, (E) endoxifen, and (Z) endoxifen] (Only Study Visit 1). Finally, buffy coat will be collected into one 1.8 mL cryo-vial. A total volume of buffy coat will be approximately 1 mL for future polymorphisms assays in tamoxifen metabolism

genes (Screen 1 and Study Visit 1). Please refer lab manual for more details on sample handling, storage and shipping.

[figure not shown]
A minimum of 15 sections will be cut from the core needle biopsy block and the surgical block, 7 for Ki67 and other IHC markers and 8 for DCIS score measurement.

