#### 10.2.3 Paraffin blocks: As each subject is enrolled, the sites will indicate on the pre-enrollment form whether the DCNB was performed at the enrolling institution, or elsewhere. If elsewhere, the name of the

hospital and contact information for the Pathology Department of that hospital will be provided. If DCNB was not done at the enrolling institution, NU-PCF NU PCF will work with the enrolling site as needed to acquire DCNB material from the site where the DCNB was performed. If DCNB was done at the enrolling institution, the study coordinator will place a request for that block to be retrieved as soon as the surgical date is known, to avoid delays caused by block retrieval.

At the end of study participation, for each subject, the paraffin blocks of the DCNB (if done at the enrolling institution) and the surgical samples will be assembled by each site as soon as the final pathology on the surgical sample has been reported. The study consent will include a statement providing permission to the hospitals involved in diagnosis and therapy (which may not be the same) to release the DCNB block and a selected surgical block to NU for study purposes. At NU PCF, the pre- and post-therapy sample blocks will be sectioned at the same time following the completion of participation of each subject. A minimum of 15 sections will be taken for: H&E, Ki67, DCIS-Score and other markers (CD68, COX2, p16), cytokeratin (CK) as epithelial classifier and at least one extra for possible repeats. All sections will be saved, vacuum-sealed and cold, until the conclusion of the study. In this way, pre- and post-therapy sections for each biomarker will be processed in the same batch.

*Slide submission for Exact Sciences DCIS-Score:* Eight unstained slides of DCBN pre-therapy block will be submitted immediately to GHI (so that the data can be used for radiation therapy decision if needed). Eight unstained slides of post-therapy block will be reserved in the NU PCF and shipped as a single batch after the study is complete and all participant samples have been received at NU.

*Institutions that do not allow release of paraffin blocks despite participant consent.* These institutions will provide unstained sections of the paraffin block as detailed above.

*Institutions that do provide paraffin blocks:* these will be returned to the institution where the sample was taken once the protocol-defined sections have been taken, typically within 3 months of submission to NU.

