**13.5.5 Analysis Plan for Exploratory Analyses.** Exploratory endpoints will be analyzed similarly to the primary and secondary endpoint analysis, driven by the hypotheses regarding treatment differences or between arms. In an additional exploratory analysis we will examine correlation between mRNA Ki67 expression and Ki67 IHC staining in a subset of study participants with both assays. Graphical tools will be used and data will be summarized using a correlation coefficient. Linear regression models with ki67 IHC assay as the outcome and mRNA ki67 assay as the predictor may be used to further examine the relationship, e.g. if the association appears nonlinear. Linear mixed effects models may also be used if paired assays are performed at both pre- and post-treatment, and will include subject as the random effect to account for the within-subject correlation between the two time points. This analysis will guide planning of future trials and is not intended as a formal endpoint for the present trial.

**Pathologic response:** Another endpoint of interest is the evaluation of pathologic response, complete (no residual DCIS in the surgical sample). If there is no residual DCIS in the surgical sample, this could mean that the DCIS was small enough at diagnosis that it was ablated by the core needle biopsy; or that the residual DCIS responded completely to therapy. With our present design it is not possible to distinguish between these two possibilities, but we will explore the possibility of pathologic complete response (pCR) in the following ways: the rate of “no residual DCIS” in clinical series and in our institution is about 10%. If we observe that the rate of no residual DCIS is doubled to 20%, we will take this as preliminary evidence of pCR.

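### 'No residual DCIS' is assessed centrally, possibly on one selected surgical block, but read against a rate of about 10% for the surgical specimen

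*Combined protocol and SAP*

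**What the plan says.** **Assessor.** Exploratory objective 3 (1.3) compares the fraction of women with no residual DCIS in the surgical specimen. Section 8.2.10 says: "This will be assessed by the study pathologist ([name]) on the surgical excisional sample". Section 8.1 places this pathologist at NU: "study pathologist at NU) will perform designation of regions of interest for digital scoring".

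**Material sent to NU.** The consent described in 3.7 is "to allow the DCNB block, and a selected surgical block to be released to Northwestern University (NU"). Section 10.2.3 likewise gives hospitals permission "to release the DCNB block and a selected surgical block to NU for study purposes". Section 10.2.1 adds: "A minimum of 15 sections will be cut from the core needle biopsy block and the surgical block". Sites that cannot release blocks send unstained sections.

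**How the result is read.** Section 2.3.3 puts the usual rate of no residual lesion at about 10% of surgical specimens. It treats a fraction above 20%, both arms pooled, as evidence of regression due to treatment. Section 13.5.5 takes the 10% from clinical series and the lead institution and states: "If we observe that the rate of no residual DCIS is doubled to 20%, we will take this as preliminary evidence of pCR".

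**Whole-specimen source.** At Study Visit 2 (7.5) sites are to: "Obtain surgical pathology report to document pathologic features including DCIS size, grade, and presence of invasion". Under 7.6.2 the pathologist signing out the case also reports how many blocks contain disease. Neither item is tied to 8.2.10.

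**The concern.** No DCIS in the submitted block and no DCIS in the specimen are different findings. The first can be a sampling result; only the second is a candidate for complete response. The plan compares its observed fraction with a specimen-level rate, but it does not say that the observed fraction is itself specimen-level.

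Section 13.5.5 offers two explanations for an absent lesion: removal by the core biopsy, or complete response. It does not mention disease that lies outside the material examined. The attrition text does not separate the cases either. For the women lost to the primary endpoint for tissue reasons, 3.2 and 13.4.2 speak of insufficient DCIS, while 13.2 speaks of absent DCIS.

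What is at stake is the pooled reading against 10%. It has no concurrent untreated control, so nothing inside the trial would reveal a sampling component.

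**Working it through.** **The plan's own figures.** The endpoint has a 10% reference and a 20% threshold, with no sample size, power or error rate. The only formal power figure belongs to the primary Ki-67 test: 40 per arm, margin 2.6, SD 5.4, one-sided alpha 0.10. It reproduces: noncentrality 2.6 / (5.4 × √(2/40)) = 2.15 on 78 df gives 80.5%. It is not in dispute here.

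**Inputs.**
- p0 = 0.10, the true specimen-level rate with no drug effect (2.3.3, 13.5.5).
- n = 90 women evaluated for study endpoints (3.2), so 81 with residual DCIS and 9 without.
- x = probability that a woman with residual DCIS has none in the material sent to NU. The documents give no value, so x is an assumption shown over a range.

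**Formula.** Apparent rate = p0 + (1 − p0)x = 0.10 + 0.90x. Twenty percent of 90 is 18 women. The chance of meeting the rule with no drug effect is an exact binomial tail: at least 18 for the 13.5.5 wording, at least 19 for the 2.3.3 wording.

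| Assumed x | Women missed (81x) | Apparent rate | P(at least 18 of 90) | P(more than 18 of 90) |
|---|---|---|---|---|
| 0% | 0 | 10.0% | 0.3% | 0.1% |
| 2% | 1.6 | 11.8% | 1.7% | 0.8% |
| 5% | 4.1 | 14.5% | 9.5% | 5.7% |
| 10% | 8.1 | 19.0% | 44.6% | 34.5% |

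An expected rate of exactly 20% needs x = 0.10/0.90 = 11.1%, that is 9 of 81 women. This value is solved backwards from the threshold; it does not predict x. Results with n = 80 or 100 are similar.

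**The opposite error.** Further sections cut at NU could show DCIS that the site did not see. If this happens in a share d of the women reported as having none, the apparent rate is 0.10(1 − d) + 0.90x. The two errors cancel when d = 9x, for example d = 18% at x = 2% or d = 45% at x = 5%. The direction of bias is therefore not fixed by logic. However, women with residual disease outnumber the others nine to one, so even a small x needs a large d to offset it.

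**The case against.** **No provision confines the assessment to one block.** Section 8.2.10 refers to the excisional sample, and the single-block wording sits in release text written mainly for Ki-67, the DCIS Score and other markers. Sections 3.7, 7.5 and 10.3.1 also speak of blocks in the plural. This stands in part. The plural can cover core plus surgical material, and nothing describes NU receiving all surgical blocks. The wording needs reconciling either way.

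**Misses may be rare.** This is the strongest objection. Under 3.7 and 10.2.3 the surgical material is requested and assembled after the final pathology report. In a trial whose primary endpoint is Ki-67 in DCIS, a site would usually choose a block with DCIS. It stands as a limit on size, though the protocol does not state that rule and a small focus could still be lost on recutting.

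**The study pathologist may consult the site report.** Nothing forbids it, but nothing requires it.

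**The consequence is limited.** The endpoint is exploratory, and 13.5.5 calls the 20% finding preliminary and concedes that the design cannot separate its two explanations. The arms are compared blind, so a miss rate equal in both would not favour either. All of this stands; only the pooled reading against 10% is exposed.

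**Stronger readings a reader might infer.** One is that missed disease will be counted as regression, or that the error can only inflate the rate. The text makes the first possible, not certain, and extra central sections work against the second. Another is to take the 10 of 100 women in 3.2 with insufficient DCIS tissue as evidence of a miss rate near 10%. That figure is not a block-miss rate, and it overlaps the women with no residual DCIS at all, whom 2.3.3 expects to be 10 to 20 percent.

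**Conclusion.** The point holds as a minor one on an exploratory endpoint. The plan names a central assessor, provides that assessor with selected material, and reads the result against a specimen-level rate without linking the two. The likely direction of error is toward apparent regression in the pooled comparison.

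The size cannot be determined from the documents. If sites nearly always send a DCIS-bearing block, the effect is small: at an assumed 2% miss rate, the chance of falsely reaching 20% is 1.7%. At 5% it is 9.5%, and at 10% it is 44.6%. These figures assume a true rate of 10%, no drug effect, 90 women, and that the 10% describes whole specimens, which is the natural reading of 2.3.3 and 13.5.5 but is not stated outright. The documents do not support a claim that the 20% threshold would be reached by sampling alone. The primary Ki-67 analysis and its power are unaffected.

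**What to change.** 1. In 8.2.10, define 'no residual DCIS' from the site's final surgical pathology report on the whole excision or mastectomy specimen together with central review. DCIS seen in either counts as residual.
2. Add a separate category for DCIS present in the specimen but absent or insufficient in the submitted material. Treat it as non-evaluable for Ki-67, and do not count it as no-residual.
3. Apply the 10% and 20% reading in 2.3.3 and 13.5.5 only to this definition, and choose one threshold: 2.3.3 requires more than 20%, 13.5.5 requires reaching 20%. With 90 women that is 19 against 18.

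The cost is endpoint wording and one derived variable from a report already obtained at Study Visit 2; no new tissue, visit or assay is needed. The downside is that site reports are not centrally standardised, which the either-source rule offsets only in part.
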